## **7.9 Axitinib Pharmacokinetic Assessments**

No baseline pharmacokinetic testing is required as the value is known to be zero in those who have not received Axitinib.

On day 15 (day of CEHPI) medication will be taken after the ultrasound examination (time zero). After this blood samples will be taken at:

- 1 hour post dose
- 2 hours post dose
- 4 hours post dose

This will be repeated on day 28 and at restaging after 8 weeks at the usual clinic appointments. If there is disease progression pharmacokinetic testing will additionally be performed.

### **7.9.1. Collection, Processing, Storage and Shipment of Pharmacokinetic Samples**

A 3 ml whole blood sample will be collected into K3-EDTA tubes to provide a minimum of 1 ml plasma for pharmacokinetic analysis and will be centrifuged (samples should be kept on ice or at 4°C until centrifugation), protected from light, at 1000 x g (at minimum) for 15 minutes at 4°C to separate the plasma. Plasma will be stored in appropriately labelled plastic amber cryovials at -20°C or lower until analysis. Plasma concentrations of Axitinib from patients on the active Axitinib treatment arm will be analysed using a validated analytical method in compliance with Pfizer standard operating procedures.

The following special precautions should be taken to minimize the rapid degradation of Axitinib in plasma when exposed to visible light:

- Following collection of blood samples, samples should be processed as soon as possible. Preferably, harvested plasma should be frozen within 1 hour of collection.
- Vacutainer tubes should be protected from light (covered completely in aluminium foil or in black protection tubes) while samples are waiting to be centrifuged to harvest plasma.
- Following centrifugation, plasma should be transferred rapidly to labelled plastic amber cryovials and stored at -20°C or lower.
- All samples should be transferred to an opaque box to protect from light exposure during storage and shipment. If a sample is inadvertently exposed to light (for 5 minutes or more), the sponsor should be notified so that the sample can be flagged for possibly spurious results.
- Once frozen, samples should not be allowed to thaw, including during shipment.
- Samples will be shipped with the completed sample inventory form and sufficient dry ice to last for at least two days.

## **8. Adverse Event Reporting**

### **8.1 Adverse Events**

All observed or volunteered adverse events regardless of treatment group or suspected causal relationship to the investigational product(s) will be reported as described in the following sections.

For all adverse events, the investigator must pursue and obtain information adequate both to determine the outcome of the adverse event and to assess whether it meets the criteria for classification as a serious adverse event (See Section Appendix 4) requiring immediate notification to Imperial College, Pfizer or its designated representative, MHRA and REC. For all adverse events, sufficient information should be obtained by the investigator to determine the causality of the adverse event. The investigator is required to assess causality. For adverse events with a causal relationship to the investigational product, follow-up by the investigator is required until the event or its sequelae resolve or stabilize at a level acceptable to the investigator, and Pfizer concurs with that assessment.

### **8.2. Reporting Period**

Serious adverse events require immediate notification to Imperial College, Pfizer or its designated representative, MHRA and REC beginning from the time that the subject provides informed consent, which is obtained prior to the subject's participation in the clinical trial, ie, prior to undergoing any trial-related procedure and/or receiving investigational product, through and including 28 calendar days after the last administration of the investigational product. Any serious adverse event occurring any time after the reporting period must be promptly reported if a causal relationship to investigational product is suspected.

- Adverse events (serious and non-serious) should be recorded on the CRF from the time the subject has taken at least one dose of trial treatment through last subject visit.
- If a subject begins a new anticancer therapy, the adverse event reporting period for non-serious adverse events ends at the time the new treatment is started. Death must be reported if it occurs during the serious adverse event reporting period after the last dose of investigational product, irrespective of any intervening treatment.

### **8.3. Definition of an Adverse Event**

An adverse event is any untoward medical occurrence in a clinical investigation subject administered a product or medical device; the event need not necessarily have a causal relationship with the treatment or usage. Examples of adverse events include but are not limited to:

- Abnormal test findings;
- Clinically significant symptoms and signs;
- Changes in physical examination findings;
- Hypersensitivity;
- Additionally, they may include the signs or symptoms resulting from:
  - Drug overdose;
  - Drug withdrawal;
  - Drug abuse;
  - Drug misuse;
  - Drug interactions;
  - Drug dependency;
  - Extravasation;
  - Exposure in utero.

Worsening of signs and symptoms of the malignancy under trial should be reported as adverse events in the appropriate section of the CRF. Disease progression assessed by measurement of malignant lesions on radiographs or other methods should not be reported as adverse events.

## **8.4. Abnormal Test Findings**

The criteria for determining whether an abnormal objective test finding should be reported as an adverse event are as follows:

Test result is associated with accompanying symptoms, and/or;

- Test result requires additional diagnostic testing or medical/surgical intervention, and/or;
- Test result leads to a change in trial dosing (outside of protocol-stipulated dose adjustments) or discontinuation from the trial, significant additional concomitant drug treatment, or other therapy, and/or;
- Test result is considered to be an adverse event by the investigator or sponsor.

Merely repeating an abnormal test, in the absence of any of the above conditions, does not constitute an adverse event. Any abnormal test result that is determined to be an error does not require reporting as an adverse event.

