## 5.8 Dosing

The recommended starting dose of Axitinib is 5 mg bd taken orally with food. Dose adjustments, including dose increase or dose reduction should be based on adverse events experienced by the individual patient. Axitinib should be taken beginning on Day 1 of the study. Doses should be taken approximately 12 hours apart continuous dosing.

Patients will be instructed to take their doses at approximately the same times each day. Patients will be instructed that if they vomit after taking a dose, that they must not take an extra dose, but instead resume subsequent doses as prescribed. Any missed dose may be taken late up to 3 hours before the next scheduled dose, otherwise, it should be skipped. If doses are missed or vomited, this must be indicated in the source documents and CRFs. Study treatment will be administered in cycles of 4 weeks in duration.

Patients who tolerate Axitinib with no adverse events related to study drug above CTCAE Grade 2 for consecutive 2-week period should have their dose increased by one dose level (see Table 4) to a maximum of 10 mg bd (unless the patient's blood pressure is >150/90 mm Hg or the patient is receiving antihypertensive medication). Patients experiencing drug reaction greater than CTCAE Grade 2 should undergo dose modification. For the patients receiving Axitinib, concomitant medications that are known to substantially inhibit the enzyme, CYP3A4, should be avoided as much as medically possible. The clinical judgment, taking into account all of these parameters, of the treating physician should be exercised in titrating Axitinib dose.

Available Axitinib Dose Levels	Dose
+2	10 mg BD
+1	7 mg BD
0 (Starting Dose)	5 mg BD
-1	3 mg BD
-2	2 mg BD

Table 4: Axitinib dose modification table

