## 5.10 Management of Axitinib-Related Adverse Events

This section contains management of adverse events except hypertension and proteinuria which are discussed in subsequent sections. Patients developing Axitinib related CTCAE Grade 1 or 2 adverse events may have their dose continued at the same dose level (See Table 4). Patients removed from treatment for intolerable toxicity should still be followed with regular tumour assessments until disease progression or start of new treatment, and

Related Adverse Events	INTERVENTION
Grade 1	Continue at same dose level
Grade 2	Continue at same dose level
Grade 3 non-haematologic treatment-related toxicity*	Decrease dose to one lower dose level
Grade 4 non-hematologic treatment-related toxicity or Grade 4 hematologic toxicity**	Interrupt dosing; re-start at one lower dose level as soon as improvement to CTCAE Grade $\leq 2$ . If patient requires dose reduction below 2 mg BD, contact sponsor for discussion prior to implementation.

for survival thereafter.

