## 9.4 Safety Analysis

Frequencies of patients experiencing at least one AE will be displayed by System Organ Class and Preferred Term according to MedDRA terminology. Detailed information collected for each AE will include a description of the event, duration, severity, seriousness, study drug relatedness, action taken, and clinical outcome. Severity of the AEs will be graded according to the NCI CTCAE version 4.03. The analysis will be performed on AEs classified as treatment emergent.

Summary tables will present the number of patients observed with AEs and corresponding percentages. The denominator used to calculate incidence percentages consists of patients receiving at least 1 dose of study medication. Within each table, the AEs will be categorized by MedDRA system organ class and preferred term. Additional subcategories will be based on event intensity and relationship to study drug. Individual patient listings will be prepared for all AE data.

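### Section 8.4 does not count a protocol-stipulated dose change as a reason to report an abnormal test as an adverse event, while 5.8 and Table 5 treat the finding behind that change as one

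*Combined protocol and SAP*

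**What the plan says.** Section 8.4 sets criteria, any one of which is enough, for reporting an abnormal test as an AE. They are:

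- accompanying symptoms;
- "Test result requires additional diagnostic testing or medical/surgical intervention, and/or";
- a bullet that begins "Test result leads to a change in trial dosing (outside of protocol-stipulated dose adjustments) or discontinuation from the trial" and goes on to cover significant added drug treatment or other therapy;
- "Test result is considered to be an adverse event by the investigator or sponsor".

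It then adds: "Merely repeating an abnormal test, in the absence of any of the above conditions, does not constitute an adverse event".

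Other sections treat the same findings differently:

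- Section 8.3 names "Abnormal test findings" among its examples of AEs.
- Section 5.8 says "Dose adjustments, including dose increase or dose reduction should be based on adverse events experienced by the individual patient".
- In Table 5 (5.10) the column of triggers is headed as related adverse events. For Grade 4 haematologic toxicity the action begins "Interrupt dosing; re-start at one lower dose level as soon as improvement to CTCAE Grade", with Grade 2 or below as the threshold.
- The Table 5 footnotes relax the action for Grade 4 lymphopenia and for asymptomatic Grade 3 or Grade 4 biochemistry. They do not mention neutrophils, platelets or haemoglobin.

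On analysis, the toxicity comparison between arms is a secondary endpoint in 2.2, specified through the type, incidence, severity, timing and seriousness of AEs. Section 9.4 says "Detailed information collected for each AE will include a description of the event, duration, severity, seriousness, study drug relatedness, action taken, and clinical outcome". Section 9.5 separately grades all haematology and chemistry values by CTCAE and displays the worst grade for each parameter.

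**The concern.** For dosing, Table 5 treats a laboratory toxicity as a related AE. For reporting, 8.4 disregards the dose action that follows. Site staff who apply 8.4 literally could leave off the AE form a finding that was severe enough to interrupt treatment, while having to report a milder one that led to a dose change outside the protocol's rules.

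The AE form feeds the secondary toxicity endpoint and the tables in 9.4. The safety committee described in the Trial Summary meets every three months to review AEs, and 8.12 assesses each AE for seriousness. A finding never entered as an AE may miss all of these steps. With about 33 Axitinib and 17 placebo patients, one or two unrecorded dose-limiting events would be visible in an AE table.

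**Working it through.** The plan gives no figure on this point, so there is none to reproduce. The check is to follow a finding through the text and then put a scale on it.

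**1. The firm case against each criterion in 8.4.** Take an asymptomatic Grade 4 neutropenia. Dosing is interrupted under Table 5, counts are repeated until recovery, and dosing restarts one level lower.

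| Criterion in 8.4 | Met? |
|---|---|
| Symptoms | No, by assumption |
| Further diagnostic testing or intervention | No, if the count is only repeated; 8.4 says a repeat alone is not enough |
| Dose change outside the protocol's rules | No; the change is the Table 5 action |
| Discontinuation, significant added drug treatment or other therapy | No, by assumption |
| Judged an AE by investigator or sponsor | Possibly; this is discretionary |

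No mandatory criterion is met. The same holds for asymptomatic Grade 4 thrombocytopenia or anaemia managed in this way.

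**2. Findings outside the gap.**

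- Proteinuria: 5.12 requires a 24-hour urine collection before any hold, which meets the additional-testing criterion.
- Any abnormality that is treated meets the intervention or added-treatment criterion.
- Grade 4 lymphopenia need not interrupt dosing (Table 5 footnote).
- Asymptomatic Grade 3 or 4 biochemistry may stay at the same dose (Table 5 footnotes). It enters the gap only if the dose is changed anyway.

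**3. Scale of the firm case.** Inputs are the Grade 4 counts in Table 2 (single-agent Axitinib, solid tumours) and 50 × 2/3 ≈ 33 Axitinib patients.

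| Parameter | Grade 4 | Rate | × 33 |
|---|---|---|---|
| Neutrophils | 12/344 | 3.49% | 1.15 |
| Haemoglobin | 3/347 | 0.86% | 0.29 |
| Platelets | 2/346 | 0.58% | 0.19 |
| White cells | 1/347 | 0.29% | 0.10 |
| Sum | | 5.22% | 1.72 |

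The chance that at least one such case arises is 1 − (1 − p)^33. With p = 0.0349 (neutrophils alone) it is 0.69. With p = 0.0522 (all four, no overlap within patients) it is 0.83. This is the chance that a case occurs, not that it goes unreported.

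**4. Chemistry, for comparison.** The Grade 3–4 chemistry rates in Table 2 sum to 27.7%, and 0.277 × 33 ≈ 9.1 patient-parameter findings. This does not measure the loss, because the footnotes allow every asymptomatic finding of this kind to continue at the same dose and 8.4 requires symptomatic ones to be reported.

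**The case against.** The strongest reply is that an investigator who applies Table 5 has already classed the value as a related AE, which satisfies the last criterion in 8.4. Section 8.3 points the same way. Read together, the sections can lead to reporting. That is a fair reading and probably what many sites would do. But it depends on judgement, and 8.4, the section written to decide the question, expressly sets the dose action aside.

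There are also other routes to reporting. Section 8.5 gives blood dyscrasias as an example of important medical events. Transfusion or colony-stimulating factors, allowed in 5.17, would count as intervention. Work-up of Grade 3 or higher toxicity under 6.2 would count if it went beyond a repeat test. These stand, and they are why 1.7 is a ceiling.

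The data are not lost either: 9.5 grades every haematology and chemistry value whatever its AE status. That stands too. However, 9.5 does not say that its tables are by arm, and it carries no relatedness, action taken or outcome.

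A reader might infer that dose-limiting laboratory toxicities as a class fall out of the arm comparison, or that about nine chemistry findings are at risk. The Table 5 footnotes, the other criteria in 8.4 and the tabulation in 9.5 do not support that. A reader might also infer a demonstrated bias in favour of Axitinib. The rule is identical in both blinded arms, Table 2 has no comparator, and the documents give no placebo laboratory rates. Any loss would fall more on whichever arm has more laboratory toxicity, but the documents do not establish how large that difference is.

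**Conclusion.** The inconsistency is real and its reach is small. Section 8.4 conflicts with 5.8 and Table 5 on whether a laboratory finding that triggers a prescribed dose change is a reportable AE, and the passages must be reconciled. Until then, reporting of an asymptomatic finding managed only by that dose change and re-testing rests on judgement.

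The firm exposure is Grade 4 haematologic toxicity other than lymphopenia, at most about 1.7 findings among about 33 Axitinib patients. This assumes that the Table 2 rates carry over to this population and that the four parameters do not overlap within patients. It becomes a loss only where the finding is asymptomatic, untreated, merely re-tested and not judged an AE. Even then the grade would appear in 9.5. The point is worth correcting because it touches a secondary endpoint and AE-based safety review at almost no cost; it does not undermine the toxicity comparison as a whole.

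**What to change.** In the dosing bullet of 8.4, delete only the parenthesis that excludes adjustments stipulated by the protocol. Keep everything else in the bullet: discontinuation from the trial, significant additional concomitant drug treatment, and other therapy. A shorter replacement sentence that left these out would remove mandatory grounds that now exist. After the deletion, any test result that leads to a reduction or interruption of study treatment is recorded as an AE, in line with 5.8 and Table 5.

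The cost is one deletion and a few extra AE entries. The change affects recording only: dose rules, sample size and analysis methods stay as they are.

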## 8.5. Serious Adverse Events

A serious adverse event or serious adverse drug reaction is any untoward medical occurrence at any dose that:

- Results in death;
- Is life-threatening (immediate risk of death);
- Requires inpatient hospitalisation or prolongation of existing hospitalisation;
- Results in persistent or significant disability/incapacity;
- Results in congenital anomaly/birth defect.

Progression of the malignancy under trial (including signs and symptoms of progression) should not be reported as a serious adverse event unless the outcome is fatal during the trial or within the safety reporting period. Hospitalisation due to signs and symptoms of disease progression should not be reported as serious adverse event. If the malignancy has a fatal outcome during the trial or within the safety reporting period, then the event leading to death must be recorded as an adverse event and as a serious adverse event with CTC Grade 5.

Medical and scientific judgment should be exercised in determining whether an event is an important medical event. An important medical event may not be immediately life-threatening and/or result in death or hospitalisation. However, if it is determined that the event may jeopardize the subject and may require intervention to prevent one of the other outcomes listed in the definition above, the important medical event should be reported as serious.

Examples of such events are intensive treatment in accident & emergency or at home for allergic bronchospasm; blood dyscrasias or convulsions that do not result in hospitalisation; or development of drug dependency or drug abuse. Adverse events reporting, including suspected serious unexpected adverse reactions, will be carried out in accordance with applicable local regulations.

## 8.6. Hospitalisation

Adverse events reported from clinical trials associated with hospitalisation, or prolongation of hospitalisation, are considered serious. Any initial admission (even if less than 24 hours) to a healthcare facility meets these criteria. Admission also includes transfer within the hospital to an acute/intensive care unit (eg, from the psychiatric wing to a medical floor, medical floor to a coronary care unit, neurological floor to a tuberculosis unit). Hospitalisation does not include the following:

CONFIDENTIAL

- Rehabilitation facilities;
- Hospice facilities;
- Respite care (eg, caregiver relief);
- Skilled nursing facilities;
- Nursing homes;
- Routine emergency room admissions;
- Same day surgeries (as outpatient/same day/ambulatory procedures).

Hospitalisation or prolongation of hospitalisation in the absence of a precipitating, clinical adverse event is not in itself a serious adverse event. Examples include:

- Admission for treatment of a pre-existing condition not associated with the development of a new adverse event or with a worsening of the pre-existing condition (eg, for work-up of persistent pre-treatment lab abnormality);
- Social admission (e.g., subject has no place to sleep);
- Administrative admission (e.g., for yearly physical exam);
- Protocol-specified admission during a clinical trial (e.g., for a procedure required by the trial protocol);
- Optional admission not associated with a precipitating clinical adverse event (e.g., for elective cosmetic surgery);
- Pre-planned treatments or surgical procedures should be noted in the baseline documentation for the entire protocol and/or for the individual subject.
- Admission exclusively for the administration of blood products.

Diagnostic and therapeutic non-invasive and invasive procedures, such as surgery, should not be reported as adverse events. However, the medical condition for which the procedure was performed should be reported if it meets the definition of an adverse event. For example, an acute appendicitis that begins during the adverse event reporting period should be reported as the adverse event, and the resulting appendectomy should be recorded as treatment of the adverse event.

## **8.7. Severity Assessment**

If required on the adverse event case report forms, the investigator will use the following definitions of severity in accordance with Cancer Therapy Evaluation Program, CTCAE version 4.03 to describe the maximum intensity of the adverse event. If the event is serious, the CTC grade reported in the adverse event CRF must be consistent with the description of CTC grade included in the narrative section of the serious adverse event report.

Grade	Clinical Description of Severity
0	No Change from Normal or Reference Range (This grade is not included in the Version 3.0 document but may be used in certain circumstances.)
1	MILD Adverse Event
2	MODERATE Adverse Event
3	SEVERE Adverse Event
4	LIFE-THREATENING OR DISABLING Adverse Event
5	DEATH RELATED TO Adverse Event

**Classification of severity of adverse events.**

## 8.8. Causality Assessment

The investigator's assessment of causality must be provided for all adverse events (serious and non-serious). An investigator's causality assessment is the determination of whether there exists a reasonable possibility that the investigational product caused or contributed to an adverse event. If the investigator's final determination of causality is unknown and the investigator does not know whether or not investigational product caused the event, then the event will be handled as "related to investigational product" for reporting purposes. If the investigator's causality assessment is "unknown but not related to investigational product", this should be clearly documented on trial records. In addition, if the investigator determines a serious adverse event is associated with trial procedures, the investigator must record this causal relationship in the source documents and CRF, as appropriate, and report such an assessment in accordance with the serious adverse event reporting requirements, if applicable.

